6.3 Study Termination Visit

The purpose of this visit is to visually inspect the skin/nares and query the subject as to any adverse events they may have encountered and to complete the study. This visit may be conducted on the morning after the completion of their final PSG or via a separate clinic visit.

6.4 Subject Selection

As noted, subjects will be recruited from existing rolls and up to 20 subjects may be enrolled with a targeted number up to 10 subjects who complete the study.

6.5 Inclusion Criteria

- Capacity and willingness to sign informed consent
- ≥ 21 years of age
- Diagnosis of mild to moderate OSA (AHI ≥ 5 and AHI ≤ 30) within 12 months of the screening visit with the 3% hypopnea criteria
- Able to tolerate using the device during a day time trial/acclimation
- Are currently using CPAP or have been prescribed CPAP and are considered CPAP non-adherent (as per either their CPAP data card and/or verbal confirmation of a diagnosis and unwillingness to use CPAP)

6.6 Exclusion Criteria

- Nasal deformities
- Severe nasal allergies
- Rhinitis or moderate nasal congestion, acute upper respiratory (including nasal, sinus or middle ear) inflammation or infection, or perforation of the ear drum
- Co-morbid sleep disorders
- Currently on a hypnotic for insomnia (who have had insomnia for more than a month and take a hypnotic on a daily basis and/or transient insomnia being treated)
- Uncontrolled or serious illness, including but not limited to: severe breathing disorders including hypercapnic respiratory failure, respiratory muscle weakness, bullous lung disease (as seen in some types of emphysema), bypassed upper airway, pneumothorax, pneumomediastinum, etc.; severe heart disease (including heart failure); or pathologically low blood pressure.
- Full Face Mask user
- Mouth breather
- Pregnant (Female subjects of child bearing age will be asked if they are and/or planning on becoming pregnant during the study; acceptable methods of birth control include birth control pills and barrier method)

7 Task and Visit Schedule Table

	Screening Visit	PSG 1	2 week in home use	PSG 2	Term. Visit*
TASK					
Informed Consent	X				
Inclusion/Exclusion Criteria	X				
CPAP usage verification, AHI(data download)	X				
Bongo Fit	X				
Demographics	X				
Vital signs	X				
Height/Weight (BMI)	X				
Medical History	X				
Concomitant Medications	X				X
PM Questionnaire/ETOH assessment		X		X	
PSG/Scoring		X		X	
Preparation for Home Use AM Tasks		X			
CRF Completion		X		X	X
Adverse Events	X	X	X	X	X
Daily Use Diary(Subject)			X		
Daily Diary (review)					X
MD CRF review/Sign off					X

*May have this visit taking place the AM of the sleep study or in the clinic.

8 Statistical Plan

The primary aim of this study is to assess objective sleep parameters while sleeping with the BONGO NASAL EPAP device (Test product). The primary endpoint to be evaluated is AHI compared to baseline data. Baseline demographic will be summarized and reported. For continuous variables such as weight, the mean, standard deviation and range will be presented. For categorical variables such as gender, the proportion of subjects in each category will be presented. Descriptive statistics for sleep study data will be reported.

8.1 Sample Size

Up to 20 subjects may be enrolled in the study with a targeted number up to 10 subjects who complete the study and are deemed evaluable. A study with 10 subjects was proposed and accepted by the FDA for the data required for inclusion within a pre-market notification (510k) submission for the Bongo.

9 Subject Compliance Monitoring

Compliance for subject participation will be assessed at each visit.

9.1 Early Withdrawal of Subjects

Although early withdrawal of subjects is not anticipated, for subjects who withdraw prior to completion of their participation, data collected to date will be included. If the withdrawal is due to medical reasons, appropriate referral to their primary care physician will be done.

9.1.1 When and How to Withdraw Subjects

A subject may withdraw from the study at any time and for any reason. Explanation of such rights will be given to the subject during the informed consent process, both verbally and in writing. If subjects decide that they no longer wish to participate in the study, they will be asked to return for a final visit. If they are unable to comply with this request, a study termination letter will be sent to their given address. A request for the study documents will be made.

9.1.2 Data Collection and Follow-up for Withdrawn Subjects

Data will cease to be collected upon subject withdrawal of informed consent; however, data collected until the time of withdrawal will be used as appropriate and will be reported in the clinical study report.

10 Risks/Benefits

Risks

Known risks include:

- Breach of confidentiality. It is possible that information regarding subjects' clinical or laboratory evaluations will be discovered by individuals outside of study personnel, despite careful steps to protect confidentiality.
- Polysomnography: Some subjects experience mild skin irritation from electrode preparation solution, electrode adhesive, or solvents used to remove electrodes. These materials can also cause eye irritation if they come into contact with the eyes. This is a standard test for ascertaining sleep disorders in clinical practice and is widely used. Sleeping within a laboratory setting may produce psychological discomfort for some subjects.
- Subjects may feel some psychological discomfort just by the fact that they are participating in research. Such concerns include confidentiality and privacy, clinical intervention or tests adverse effects from the investigational product.

Possible Anticipated Device adverse events include:

- Headache
- Sinus Allergy
- Irritation of the nares from the nasal inserts

Benefits

Benefits include evaluation of current apnea status

11 Safety and Adverse Events

11.1 Definitions

Unanticipated Problems Involving Risk to Subjects or Others

Any incident, experience, or outcome that meets all of the following criteria:

- Unexpected in nature, severity, or frequency (i.e. not described in study-related documents such as the IRB-approved protocol or consent form, the investigators brochure, etc...)
- Related or possibly related to participation in the research (i.e. possibly related means there is a reasonable possibility that the incident experience, or outcome may have been caused by the procedures involved in the research)
- Suggests that the research places subjects or others at greater risk of harm (including physical, psychological, economic, or social harm).

Unanticipated Adverse Device Effect

An Unanticipated Adverse Device Effect is any serious adverse effect on health or safety, or any life-threatening problem or death caused by or associated with a product, if that effect, problem, or death was not previously identified in nature, severity, or degree of incidence in the investigational plan or application (including a supplementary plan or application), or any other unanticipated serious problem associated with a product that relates to the rights, safety, or welfare of subjects.

Serious injury

Any injury or illness that is any one of the following:

- life-threatening
- results in permanent impairment of a body function or permanent damage to body structure
- necessitates medical or surgical intervention to preclude permanent impairment of a body function or permanent damage to a body structure

Adverse Event

An **adverse event** (AE) is any symptom, sign, illness or experience that develops or worsens in severity during the course of the study. Intercurrent illnesses or injuries should be regarded as adverse events. Abnormal results of diagnostic procedures are considered to be adverse events if the abnormality:

- results in study withdrawal
- is associated with a serious adverse Product effect
- is associated with clinical signs or symptoms
- leads to additional treatment or to further diagnostic tests
- is considered by the investigator to be of clinical significance

11.2 Recording of Adverse Device Effects

At each contact with the subject, adverse events will be assessed. Data will be documented on an adverse event form and the subject chart. Any and all clearly study related signs, symptoms, and abnormal diagnostic procedures results should be recorded in the source document; however, events related to each other should be grouped under one diagnosis.

All adverse Product effects occurring during the study period will be recorded. The clinical course of each event will be followed until resolution or stabilization or until it has been determined that the study treatment or participation is not the cause. Serious adverse Product effects that are still ongoing at the end of the study period will be followed to determine the final outcome. Any serious adverse Product effects that occur after the study period should be recorded and reported promptly (see section 8.3 below).

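### Section 11.2 limits source recording to clearly study-related findings, which is inconsistent with the all-causality adverse event definition in 11.1 and could lead to under-recording of headache and sinus allergy

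*Combined protocol and SAP*

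**What the plan says.** Section 11.1 defines an adverse event by occurrence, not cause: it "is any symptom, sign, illness or experience that develops or worsens in severity during the course of the study". It adds: "Intercurrent illnesses or injuries should be regarded as adverse events".

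Section 11.2 then gives its recording instructions in this order:

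- Ascertainment: "At each contact with the subject, adverse events will be assessed".
- Documentation: "Data will be documented on an adverse event form and the subject chart".
- Source recording: "Any and all clearly study related signs, symptoms, and abnormal diagnostic procedures results should be recorded in the source document". The sentence goes on to ask that events related to each other be grouped under one diagnosis.
- Study-period recording: "All adverse Product effects occurring during the study period will be recorded".
- Follow-up: the course of each event is followed to resolution or stabilization, or "until it has been determined that the study treatment or participation is not the cause".

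Section 10 lists three possible anticipated device events: headache, sinus allergy, and irritation of the nares from the inserts.

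**The concern.** The source-recording sentence makes a causality judgement a condition of entry, and sets it high. The protocol gives no criteria for *clearly* and no relatedness scale. The judgement would fall to site staff who know the treatment and have no comparator group to set against it.

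Headache and sinus allergy are common complaints that can seldom be tied firmly to a device in one person. Section 6.2 shows how this could arise. A subject who arrives for a PSG with nasal congestion or allergy is sent home until it resolves, and that text does not mention adverse event recording. Staff who follow the 11.2 sentence literally could treat the episode as background.

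The data are intended for a 510(k) submission (section 4.1) and the target is up to 10 completers (section 8.1), so one or two missing events would change the safety picture. Monitoring is expected at least once, most likely at the end of the study (section 14.1). That is late to recover an event that was not written down when it happened.

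**Working it through.** The plan states no figure on this point, so there is none to reproduce. The check is mainly a comparison of text.

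**Step 1: the standards side by side.**

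| Place | What is captured | Relatedness condition |
|---|---|---|
| 11.1, adverse event | Anything that develops or worsens, including intercurrent illness | None |
| 11.2, opening two sentences | Adverse events, on form and chart | None |
| 11.2, third sentence | Signs, symptoms, abnormal results, in the source document | Clearly study related |
| 11.2, second paragraph | Adverse Product effects | Implied by the term, which 11.1 does not define |
| 11.1, unanticipated problems | Incidents, experiences, outcomes | Related or possibly related |

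The third row is narrower than the first two. It is also stricter than the last, where "possibly related means there is a reasonable possibility that the incident experience, or outcome may have been caused by the procedures involved in the research".

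**Step 2: can the third sentence be confined to a separate record?** Not with confidence. Section 13.2 lists case report forms and investigator notes among possible source documents. The adverse event form may therefore itself be a source document, in which case one record is subject to two rules.

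**Step 3: consistency with follow-up.** Following an event until the study is ruled out as its cause presupposes that events of undetermined cause are already on record. A clearly-related rule would not put them there.

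**Step 4: which anticipated events are exposed?** Headache and sinus allergy are. Irritation of the nares is less so: it is local, section 10 attributes it to the inserts, and section 6.3 has the nares inspected at the termination visit.

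**Step 5: conditional illustration.** This applies only if a site uses the sentence as a filter on what it records. Let n be the number of subjects (10 completers or 20 enrolled, section 8.1), p the true proportion with the event, and c the share of cases judged clearly related. Both p and c are assumptions. Then

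P(at least one recorded) = 1 − (1 − pc)^n.

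For n = 10 and p = 0.20:

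- c = 1: 1 − 0.80^10 = 0.893
- c = 0.75: 1 − 0.85^10 = 0.803
- c = 0.5: 1 − 0.90^10 = 0.651
- c = 0.25: 1 − 0.95^10 = 0.401

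Other cases, in the same order of c:

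- n = 10, p = 0.10: 0.651, 0.541, 0.401, 0.224
- n = 20, p = 0.20: 0.988, 0.961, 0.878, 0.642

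The expected number of recorded cases is npc. For n = 10 and p = 0.20 it falls from 2.0 at c = 1 to 1.0 at c = 0.5.

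**The case against.** A reader might infer that only clearly related events are recorded, that under-counting will follow, and that ambiguous events leave no source entry. The documents do not support this.

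- Section 11.2 does not say *only*. The two preceding sentences put adverse events on the form and in the subject chart with no causality test, so a source entry may well exist.
- Other sections ask for any adverse event. Section 6.2 tells subjects to call the site, section 6.3 queries them at termination, the section 7 schedule marks adverse events in every column including home use, and section 11.3.1 sends any event noted by the investigator to the sponsor.
- The sentence can be read as guidance on detailing and grouping individual signs and test results, added to the general rule. On that reading it is loose drafting, not a flat contradiction.
- The possibly-related threshold belongs to unanticipated problems, which have their own form and narrative in 11.3.1. They do not depend on this sentence to be documented.
- Section 14.1 says at least one monitoring visit and allows periodic monitoring, so a single visit is not fixed.

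All of this stands, and it limits the point to a risk that depends on how the site reads 11.2. It does not remove the inconsistency. The third sentence is the one that says which signs and symptoms belong in the source document. The sponsor-reporting rule operates only on events already noted. The breadth of the other sections suggests that all-causality capture was intended, in which case the qualifier serves no evident purpose.

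**Conclusion.** The inconsistency is established from the text: the source-recording sentence in 11.2 is narrower than the 11.1 definition and than the opening of 11.2 itself. That it would reduce the recorded events is possible but not shown. It requires staff to apply the phrase as a filter, and the illustrative probabilities rest on assumed event rates and an assumed share judged clearly related. The exposure is confined mainly to headache and sinus allergy. This is a wording defect that should be corrected, because the safety data are few and uncontrolled and the remedy is nearly free. It does not call the design or the primary endpoint into question.

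**What to change.** In section 11.2:

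- Delete the words *clearly study related*. State that every adverse event meeting the 11.1 definition is recorded in the source document and on the adverse event form, whatever its cause. The tie to 11.1 matters: deletion alone would call for every abnormal test result, whereas 11.1 limits these to five circumstances.
- State that relatedness is judged separately, after recording.
- In "All adverse Product effects occurring during the study period will be recorded", replace adverse Product effects with adverse events.
- Keep the instruction on grouping under one diagnosis.

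Report all events and related events. Section 8 names no adverse event summary, so one sentence there would suffice. A graded relatedness scale, severity, onset date and valve in use would be useful fields but are optional. The form is not among the documents and may already contain them.

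The cost is a wording change with no effect on visits, sample size or the primary analysis. The downside is a slightly longer and less favourable-looking event listing.

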11.3 Reporting of Adverse Device Effects and Unanticipated Problems

11.3.1 Investigator reporting: Notifying the study sponsor

Any events which are noted by the investigator will be reported to the sponsor not more than 10 days after learning of the event.

Sponsor contact information for reporting purposes

Report adverse Product effects by phone and facsimile to:

InnoMed Healthscience
[contact] [contact] fax

Adverse Product Effects

Any adverse Product effect that results in serious injury or death, and any type of unanticipated adverse Product effect, regardless of seriousness or severity, must be reported to the study sponsor by telephone within 24 hours of the event.

Within the following 48 hours, the investigator shall provide further information, as applicable, on the unanticipated Product event or the unanticipated problem in the form of a written narrative. This should include a copy of the completed Unanticipated Problem form, and any other diagnostic information that will assist the understanding of the event. Significant new information on ongoing unanticipated adverse Product effects shall be provided promptly to the study sponsor.

Withdrawal of IRB approval

An investigator shall report to the sponsor a withdrawal of approval by the investigator's reviewing IRB as soon as possible, but no later than 5 working days from the IRB notification of withdrawal of approval.

11.3.2 Investigator reporting: Notifying the IRB

This study will be submitted for review by a central IRB. Reporting of any reportable events will conform to IRB policy and procedures

Adverse Product Effects

All unanticipated Product effects, and all adverse Product effects resulting in research subject death or injury reported by the investigator to the study Sponsor must also be reported to the investigator's local IRB in accordance with their reporting requirements, though no later than 10 working days.

Protocol Deviations

Any protocol deviations initiated without Sponsor and/or the investigator's IRB approval that may affect the scientific soundness of the study, or affect the rights, safety, or welfare of study subjects, must be reported to the Sponsor and to the investigator's IRB as soon as a possible, but no later than 5 working days of the protocol deviation.

Reporting Process

Report unanticipated problems as defined above to the IRB using the form: as indicated on the IRB web site/portal or as a written report of the event (including a description of the event with information regarding its fulfillment of the above criteria, follow-up/resolution and need for revision to consent form and/or other study documentation).

Copies of each report and documentation of IRB notification and receipt will be kept in the Clinical Investigator's study file.

12 Receiving, Storage, Dispensing and Return

12.1 Packaging

A "fitting kit" consisting of a full set of BONGO devices with the R1 resistor will be available to study staff for sizing and acclimation purposes. These devices will be cleaned according to standard practice for cleaning CPAP masks following the facility procedures. Devices will be cleaned after each subject.

For each subject, BONGO nasal inserts of their selected size with both resistors values (R1 and R2) will be provided. If R2 is needed, the sleep technologist will replace the Bongo R1 device with the Bongo R2 device.

12.2 Receipt of Study Product

Sites will receive and log in all investigational products according to routine practices. Devices will be shipped with appropriate labeling and shipped from InnoMed.

12.3 Dispensing of Study Product

Product will be dispensed only to those subjects qualified to receive them. A device distribution log will be maintained at the site.

12.4 Return of Study Product

Used devices shall be re-inserted into their original packaging and returned to InnoMed at the completion of the study and documented on the appropriate logs.

13 Data Handling and Record Keeping

13.1 Confidentiality

Information about study subjects will be kept confidential and managed according to the requirements of the Health Insurance Portability and Accountability Act of 1996 (HIPAA). The Protected Health Information (PHI) collected during this study is related to general health and sleep. No additional information will be collected regarding the subject's PHI.

Review of data will be allocated to study personnel on a "need to know" basis. An enrolled subject will be assigned a unique patient ID number. Study personnel will use the patient ID number to identify all subject data on case report forms.

In the event that a subject revokes authorization to collect or use PHI, the investigator, by regulation, retains the ability to use all information collected prior to the revocation of subject authorization. For subjects that have revoked authorization to collect or use PHI, attempts should be made to obtain permission to collect at least vital status at the end of their scheduled study period.

13.2 Source Documents

Source documents may include the following

- Investigator/Designee Note form
- Case report forms
- Data from the CPAP downloads
- Data from the Polysomnogram
- Self-completed questionnaires

13.3 Case Report Forms

All case report forms (CRF) will be completed in their entirety (i.e. each field filled out and or noted as not applicable). For any errors, standard good clinical practice includes the following: Each error will be crossed out with a single line, dated and initialed by the person who made the correction. Queries by the monitor will be generated for forms not completed and/or illegible

13.4 Records Retention

Records will be kept at the investigational research site for a period of no less than 2 years. Data will be kept in a secure and locked environment. It is acceptable to maintain records at an off-site facility which can be accessed within a reasonable period of time (i.e. 2 days after request).

14 Study Monitoring, Auditing, and Inspecting

14.1 Study Quality/Monitoring Plan

A study start-up meeting will be conducted to ensure all study staff are informed regarding conduct of the study and trained on the investigational product and any additional study tasks or procedures that are unique to the study. A study manual of operations (MOP) will be provided to the site to enhance GCP of the site.

It is anticipated that this study will be monitored at least once during the course of the study, most likely at the end of the study for all subjects enrolled. However, periodic monitoring may be conducted if deemed necessary.

